6.2 Procedures During Treatment

Patients receiving study treatment will be followed every 2 weeks and the following will be done (unless otherwise indicated).

- History and physical exam (\pm 3 days).
- Laboratory evaluation (\pm 3 days): Hematologic profile (CBC with differential). Biochemical profile. Does not need to repeat for C1D1 if performed within 7 days.
- Thyroid function testing will be done every cycle on day 1 (\pm 3 days) and day 29 (\pm 3 days) for subjects receiving nivolumab. Does not need to repeat on C1D1.
- Tumor imaging will be performed every 8 weeks (\pm 7 days).
- NETSPOT[®] PET scan on cycle 2 day 1 (\pm 3 days) to assess the metabolic response.
- Serum or urine beta-hCG for female patients of childbearing age within 24 hours prior to the administration of ¹⁷⁷Lu-DOTA⁰-Tyr³-Octreotate.

Patients randomized to observation will be followed every 4 weeks and the following will be done.

- History and physical exam (\pm 3 days).
- Laboratory evaluation (\pm 3 days): Hematologic and biochemical profile. Laboratory evaluation can be performed within 3 days prior to clinic visit.
- Tumor imaging will be performed every 8 weeks (\pm 7 days).

After 30 days (\pm 7 days) from treatment termination, the following will be obtained if the patient is available:

- History and physical exam.
- Laboratory evaluation: Hematologic and biochemical profile. Thyroid function testing.

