5.3.1 General Recommendations for Evaluation of Toxicities and Dose Delays/Modifications

Any patient who receives treatment on this protocol will be evaluable for toxicity. Toxicity will be assessed according to the NCI Common Toxicity Criteria for Adverse Events (CTCAE), version 4.03. Dose delays or dose modifications should be made according to the system showing the greatest degree of toxicity. Once the patient has a dose reduction due to toxicity, the dose will not

be re-escalated. Dose delays and dose modifications will be made using the following recommendations. At the discretion of the investigator, the study drugs may be held or dose modified independently if the observed AE is attributed to only one of the study drugs, while the patient continued to receive the drug not associated with the observed AE. For example, if the patient develops immune-related adverse events, nivolumab may be held following guidelines in section 5.3.5 while the patient continues to receive $^{177}\text{Lu-DOTA}^0\text{-Tyr}^3\text{-Octreotate}$. If the patient develops hematologic adverse events that are frequently associated with $^{177}\text{Lu-DOTA}^0\text{-Tyr}^3\text{-Octreotate}$, but rarely associated with nivolumab (e.g. thrombocytopenia), $^{177}\text{Lu-DOTA}^0\text{-Tyr}^3\text{-Octreotate}$ may be held while the patient continues on nivolumab. If the observed toxicity is attributable to both drugs, both drugs will be held.

Dose modifications for $^{177}\text{Lu-DOTA}^0\text{-Tyr}^3\text{-Octreotate}$ are permitted according to the table below.

Dose Level (DL)	$^{177}\text{Lu-DOTA}^0\text{-Tyr}^3\text{-Octreotate}$ (IV)
Level 1	3.7 GBq (100 mCi) every 8 weeks
Level 2	7.4 GBq (200 mCi) every 8 weeks

No dose modifications are allowed for nivolumab.

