5.3.2 Hematologic Toxicities

Table 3. General Recommendations for Dose Modifications and Management of Hematological Toxicities

Adverse Event or Observation	Management
ANC* $\geq 1,000/\text{mm}^3$ AND Platelets** $\geq 75,000/\text{mm}^3$ AND Hemoglobin*** $\geq 8 \text{ g/dL}$	Maintain dose
ANC $< 1,000/\text{mm}^3$ OR Platelets $< 75,000/\text{mm}^3$ OR Hemoglobin $< 8 \text{ g/dL}$	On first occurrence, hold the drug(s) causing the toxicity up to 21 days until ANC $\geq 1,000/\text{mm}^3$, platelets $\geq 75,000/\text{mm}^3$, hemoglobin $\geq 9 \text{ g/dL}$. The subinvestigator and/or PI will determine whether one or both drugs are responsible for an observed toxicity and will initiate appropriate medical therapy and no change in dose upon re-initiation.

	
On second occurrence, hold the drug(s) causing the toxicity up to 21 days until ANC \geq 1,000/mm³, platelets \geq 75,000/mm³, hemoglobin \geq 9 g/dL. Treatment with ¹⁷⁷Lu-DOTA⁰-Tyr³-Octreotate may be restarted one dose level lower.
 
Patient who have not recovered to ANC \geq 1,000/mm³, platelets \geq 75,000/mm³, hemoglobin \geq 9 g/dL after 21 days should be removed from the drug causing the toxicity.

Grade 4 hematologic AE	
On first occurrence, hold the drug(s) causing the toxicity up to 21 days until ANC \geq 1,000/mm³, platelets \geq 75,000/mm³, hemoglobin \geq 9 g/dL. Treatment with ¹⁷⁷Lu-DOTA⁰-Tyr³-Octreotate may be restarted one dose level lower.
 
On second occurrence, discontinue the drug(s) causing the toxicity. Follow patient until resolution and/or stabilization of toxicity.
 
Patient who have not recovered to ANC \geq 1,000/mm³, platelets \geq 75,000/mm³, hemoglobin \geq 9 g/dL after 21 days should be removed from the drug causing the toxicity.

*ANC: Absolute neutrophil count. Growth factors to prevent neutropenia will not be administered prophylactically, but can be used during a drug hold to assist the recovery.

** Thrombocytopenia will be treated conservatively. In the absence of bleeding, or a necessary invasive procedure, platelet transfusions should be given for a platelet count \leq 10,000/mm³. If invasive procedure(s) is (are) planned, or the patient develops bleeding, platelet transfusions should be administered in accordance with the standard of practice, usually maintaining a platelet count above 50,000/mm³.

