6.0 STUDY PROCEDURES

6.1 Screening/Baseline Procedures

Subjects who meet all eligibility criteria will be enrolled in the study. Assessments performed exclusively to determine eligibility for this study will be done after obtaining informed consent. Assessments performed for clinical indications (not exclusively to determine study eligibility) may be used for baseline values even if the studies were done before informed consent was obtained. All screening procedures must be performed within 4 weeks prior to starting study drugs, unless otherwise stated. The screening procedures include:

- Complete history and physical examination including vital signs, height, weight and ECOG performance score (see appendix C).
- Baseline imaging studies: Patients should have a baseline radiographical evaluation with computed tomography (CT) scan of the chest/abdomen/pelvis, MRI or CT of the brain, and FDG-PET (skull base to mid-thigh). Two NETSPOT[®] PET scans will be performed, the first one within 4 weeks before the start of chemotherapy (preferable) or as soon as possible after initiation of chemotherapy. This scan will be used to evaluate SSTR2 expression and the patient's eligibility for the study. The second NETSPOT[®] PET scan will be conducted as far as possible from the end of chemotherapy (ideally within 1 week before the start of study treatment). This scan will be used for exploratory analysis on eventual SSTR2 expression modification with chemotherapy. If a patient presents after completion of chemotherapy and did not have a NETSPOT[®] PET scan performed before or during chemotherapy, a NETSPOT[®] PET scan will be obtained to determine the patient's eligibility. The participating centers of the proposed study will follow the approved reconstitution and quality control procedures for [⁶⁸Ga]-DOTATE, and will use the qualified Ge-68/Ga-68 generator. Outside imaging studies will be accepted at the discretion of the PI.
- Electrocardiogram (EKG)

- Laboratory evaluation (baseline tests to be obtained within two weeks prior to starting treatment unless otherwise noted)
 - Hematological Profile: Complete blood count (CBC) with differential and platelet count, prothrombin time/international normalized ratio (PT/INR), activated partial thromboplastin time (aPTT).

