Amylase	X										
Lipase	X										
HBsAg ^e	X										
anti-HCV ^e	X										
anti-HIV ^e	X										
Pregnancy test ^f	X		X ^f				X ^f				
Tumor biopsy	X ^g	Optional at the time of progression									
Nivolumab ^h		X	X	X	X	X	X	X	X		
¹⁷⁷ Lu-DOTA ⁰ -Tyr ³ -Octreotate			X				X ^h				
Long-term follow up including survival											X ⁱ

- a: Initial tumor assessment will be performed at C2 D1 (\pm 7 days) and every 8 weeks (\pm 7 days) thereafter.
 - b: Refer to section 6.1 for details
 - c: On treatment Netspot only on cycle 2 day 1 (\pm 3 days)
 - d: Thyroid function testing will be done every cycle on day 1 (\pm 3 days) and day 29 (\pm 3 days). Does not need to repeat on C1D1.
 - e: Within three months prior to starting study treatment
 - f: Only for women of child bearing potential (WOCBP). Within 24 hours prior to the administration of $^{177}\text{Lu-DOTA}^0\text{-Tyr}^3\text{-Octreotate}$.
 - g: Optional. Utilization of archival tissue will be allowed.
 - h: May be given one day earlier or delayed up to 1 week. $^{177}\text{Lu-DOTA}^0\text{-Tyr}^3\text{-Octreotate}$ will only be given for 4 cycles.
 - i: Annually for two years
 - j: C1D1 laboratory tests do not need to be repeated if the screening laboratory tests were done within 7 days from C1D1.
- * Refer to section 6.2 for details about time windows within which each procedure should be performed.

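### After cycle 1 day 1, the ±3-day laboratory window lets the blood count and chemistry be drawn after the infusion they should inform, most importantly at the four Lutathera doses

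*Combined protocol and SAP*

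**What the plan says.** All references are to the combined protocol and SAP.

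- **Window.** For patients on treatment, section 6.2 gives "Laboratory evaluation (\pm 3 days): Hematologic profile (CBC with differential" and the biochemical profile at every two-weekly visit. The window is symmetric.
- **Calendar.** Appendix D places both tests on days 1, 15, 29 and 43, which are the infusion days. For timing it says only "Refer to section 6.2 for details about time windows within which each procedure should be performed".
- **C1D1.** Section 6.1 asks for "baseline tests to be obtained within two weeks prior to starting treatment unless otherwise noted". A calendar footnote adds "C1D1 laboratory tests do not need to be repeated if the screening laboratory tests were done within 7 days from C1D1".
- **Hold rules.** Table 3 (section 5.3.2) keeps the dose only if ANC, platelets and hemoglobin all meet stated levels. Otherwise the rule begins "On first occurrence, hold the drug(s) causing the toxicity up to 21 days until ANC" and lists recovery levels. Table 4 acts on toxicity grade. Table 6 delays or stops nivolumab for hepatic and renal events, which are detected through chemistry. None of the three says how recent the routine result must be.
- **A pre-dose window elsewhere.** Section 6.2 asks for "Serum or urine beta-hCG for female patients of childbearing age within 24 hours prior to the administration of" Lutathera.
- **Dosing windows.** Sections 5.2.1 and 5.2.2 let each drug be given from one day early to one week late. Neither section includes a laboratory check before infusion.

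**The concern.** The hold rules assume a count that is current when the dose is given, but the window does not secure one. A site that infuses on day 15 and draws the blood on day 18 has met section 6.2. Suppose a patient's platelets fell below 75,000/mm³ since the previous visit. That patient could then receive a dose that Table 3 would have held.

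This matters most for Lutathera. The dose cannot be taken back, there are only four, and a low count found afterwards protects only the next dose, about 8 weeks later. At nivolumab-only visits the issue is mainly chemistry, or counts attributed to nivolumab. Section 5.3.1 describes hematologic events as often linked to Lutathera "but rarely associated with nivolumab (e.g. thrombocytopenia") and lets nivolumab continue in that case.

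**Working it through.** The plan states no figure to reproduce, so the check is day arithmetic on the stated windows.

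**Inputs.** Visits every 14 days; sampling offset s from −3 to +3 days (section 6.2); infusion offset d from −1 to +7 days (section 5.2); C1D1 tests waived if screening tests are 0 to 7 days old (Appendix D); Lutathera on day 15 of cycles 1 to 4 (section 5.2.1 and Appendix D).

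**Assumption.** The protocol does not say whether the ±3 days run from the nominal day or the actual infusion day. The main figures use the nominal day.

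**1. Visits affected.** Four cycles × 4 visits = 16. Less C1D1, 15 dosing visits remain: 4 with Lutathera and 15 − 4 = 11 with nivolumab only.

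**2. Permitted sampling days after the infusion (s > d), out of 7.**

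| Infusion offset d | Days after infusion |
|---|---|
| −1 | 4 |
| 0 | 3 |
| +1 | 2 |
| +2 | 1 |
| +3 or later | 0 |

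If the window instead moves with the actual infusion, the count is 3 of 7 whatever the shift. The gap exists under either anchor.

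**3. Age of the latest scheduled result when the current sample follows the infusion.** Age = 14 + d − p, where p is the offset of the previous sample.

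- Infusion on the nominal day, p from −3 to +3: 14 − 3 = 11 to 14 + 3 = 17 days.
- C1D15 with C1D1 tests waived, p from −7 to 0: 14 − 0 = 14 to 14 + 7 = 21 days.
- With d from −1 to +2, the shifts that still leave a permitted sampling day afterwards: 14 − 1 − 3 = 10 to 14 + 2 + 3 = 19 days. With the waiver: 14 − 1 − 0 = 13 to 14 + 2 + 7 = 23 days.

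These are permitted extremes. They ignore section 5.2.2's re-timing of later nivolumab doses after a shift.

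**4. What already limits the risk.**

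- *Lutathera doses 2 to 4.* Between one day 15 and the next, tests fall due on day 29, day 43 and the next day 1. The last is nominally 56 − 14 = 42 days after the previous Lutathera dose. A missed hold needs acceptable results there and a new fall in the following two weeks.
- *C1D15.* No Lutathera has yet been given. Treatment starts at least 14 days after chemotherapy (sections 4.1.1.4 and 4.2.1.5), so C1D15 is nominally at least 14 + 14 = 28 days after it. Entry required ANC above 1.5 × 10⁹/L and platelets above 100 × 10⁹/L, against hold thresholds of 1,000/mm³ and 75,000/mm³.
- *C1D1.* Baseline tests must precede treatment.
- *Known toxicity.* Dose-limiting toxicity is followed weekly (section 5.1.1.1), and Table 6 sets more frequent hepatic and renal checks once an event is recognized. Restart after a Table 3 hold already requires recovered counts.

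**5. How much of Table 4 is involved.** A related grade 2 event leads to a hold only after more than 7 days despite maximal intervention, so one fresh grade 2 value cannot trigger it. At grade 3 or higher, asymptomatic GGT rises and promptly corrected asymptomatic electrolyte changes are excluded. What remains is other laboratory events of grade 3 or higher. Hepatic and renal immune-related holds come under Table 6.

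**The case against.** The strongest reply is that Table 3 already makes dosing conditional on counts and the calendar puts the tests on the dosing day. Read together, ±3 days is a visit tolerance, and a sensible site would check before infusing. Much of this stands. The window is permissive and does not tell anyone to test late, and Table 3 implies that a count is known. But the text does not say that the count must belong to the current visit. Dosing on the previous visit's result would therefore not be a deviation, and monitors could not detect it as one across six or seven institutions.

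A reader might infer from section 6.2's observation-arm sentence, "Laboratory evaluation can be performed within 3 days prior to clinic visit", that a dosing safeguard was written for the wrong arm. The documents do not support that. The observation arm has the same ±3-day window and no dose to hold, so the sentence is a scheduling convenience. Only the pregnancy-test contrast is relevant.

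A reader might also infer that the equally wide examination window is a comparable gap. The calendar schedules an adverse event assessment on every dosing day, and section 8.1.1 counts clinically significant examination findings as adverse events, so that part is largely covered.

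**Conclusion.** The gap is real and worth closing, but narrow. After C1D1 the plan permits the blood count and chemistry for a dosing visit to be drawn after the infusion. The decision to start a Table 3 hold, a Table 4 hold for a laboratory event of grade 3 or higher, or a hepatic or renal Table 6 hold may then rest on the previous visit's result. The figures of 3 in 7 sampling days and 11 to 17 days (14 to 21 at C1D15 with the waiver) assume a nominal-day anchor and a nominal-day infusion.

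It would be wrong to infer that patients will routinely be dosed on counts two to three weeks old. The documents give no basis for a frequency, and the residual case is a new, asymptomatic laboratory change since the last visit. It would also be wrong to infer any effect on sample size, the progression-free survival analysis or the definition of dose-limiting toxicity.

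The check covers sections 5.1 to 5.3, 6.1, 6.2 and Appendix D. The end of Appendix E and part of Appendix F could not be read.

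**What to change.** In section 6.2 and in one Appendix D footnote, for dosing visits after C1D1, replace ±3 days for the blood count and chemistry with: within 3 days before the infusion (before the first infusion if both drugs are given at that visit), with results reviewed against Tables 3, 4 and 6 before dosing. Leave the examination window, the thresholds and the C1D1 waiver as they are. The result used is then 0 to 3 days old.

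Costs:

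- **Repeat tests** when d − s > 3: from a 4-day delay if the sample was drawn on the nominal day, and from a 1-day delay if it was drawn on day −3.
- **Day 15.** One set serves both drugs when they are given together. Their separate windows allow them to be up to 7 − (−1) = 8 days apart, which may need a second set.
- **Vial timing.** The single-dose vial is calibrated for infusion 24 or 48 hours after production (section 9.1.1) and expires at 72 hours (Appendix G), leaving 48 or 24 hours after calibration. A sample 72 hours before infusion leaves 72 − 24 = 48 or 72 − 48 = 24 hours to obtain the result before production. This assumes that the order lead time, which the documents do not give, is no longer than that.

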5.1.2 Phase II

The phase II portion will consist of patients with ES-SCLC who completed platinum based standard first-line chemotherapy (e.g. 4-6 cycles of platinum plus etoposide or irinotecan) without disease progression (responders plus stable disease) at the time of initiation of the combination therapy with $^{177}\text{Lu-DOTA}^0\text{-Tyr}^3\text{-Octreotate}$ and nivolumab. Eligible patients will then be randomly allocated in two arms: one will be treated with the combination of $^{177}\text{Lu-DOTA}^0\text{-Tyr}^3\text{-}$

Octreotate and nivolumab, and the other arm will continue be followed (observation) after completion the standard chemotherapy treatment.

Randomization:

Patients who do not receive radiotherapy after chemotherapy

- The randomization must occur within 6 weeks of the last chemotherapy cycle.
- The study treatment must start within 2 weeks from randomization, but no less than 2 weeks from last dose of chemotherapy.

Patients who receive radiotherapy (including prophylactic cranial radiation and/or thoracic radiation) after chemotherapy

- Randomization must occur at least 8 weeks after completion of radiation therapy but within 12 weeks after completion of radiation therapy.

Randomization process:

- OnCore will be used as statistical center and the randomization algorithm will be developed by the study biostatistician.
- The project management department will be the first point of contact for assessment through email.

Courses are defined as 56 days of dosing. Nivolumab will be given until progressive disease, patient withdrawal, or toxicities. For patients randomized to the observation group, cross-over at the time of disease progression will be allowed, since the primary endpoint is PFS and not OS.

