8.3 Reporting Requirements for Adverse Events

Participating investigators (all sites) must report all serious adverse events to the Sponsor-Investigator within **24 hours** of discovery or notification of the event. The participating investigator must also provide follow-up information on the SAE until final resolution. The Sponsor-Investigator can be contacted at [name], E-mail: [contact], [contact] with CC to [contact] and CC to sub-investigator [name], E-mail: [contact].

The Sponsor-Investigator will review the SAE and report the event to the FDA, external collaborator(s), IND manufacturer, and IRB as applicable as described below.

It is the Sponsor-Investigator's responsibility (e.g. lead site PI) to ensure that all serious adverse events that occur on the study (e.g. all SAEs that occur at each enrolling institution) are reported to all participating sites.

*After informed consent has been obtained but prior to initiation of study treatment, only serious adverse events caused by a protocol-mandated intervention (e.g., invasive procedures such as biopsies) should be reported.

**After initiation of study treatment, all adverse events will be reported until 30 days after the last dose of study treatment or last observation follow-up visit or until initiation of new systemic anti-cancer therapy, whichever occurs first, and serious adverse events will continue to be reported until 90 days after the last dose of study treatment or last observation follow-up visit or until initiation of new systemic anti-cancer therapy, whichever occurs first.

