11.3 Data Analyses Plans

PFS will be defined as the time from random assignment to disease progression or death from any cause, whichever comes first. OS will be defined as the time from random assignment to death from any cause; living patients will be censored at the date of last follow-up. Survival will be estimated and plotted by the Kaplan–Meier method. In addition, the median progression-free and overall survival times will be reported along with the 95% confidence intervals. The cox proportional hazards regression model will be used to obtain hazard ratios (HRs) and the log-rank test will be utilized to compare survival estimates between the maintenance group and the control observation group. Secondary endpoints will be analyzed when the required number of events for the primary endpoint (PFS) has been met. The DCR is defined as the proportion of patients with a best overall response of CR, PR, or SD. The ORR is defined as the proportion of patients with a best overall response of CR or PR. All randomized subjects will consist of the safety population. This population will be used for all summaries of safety data (AEs, concomitant medications, laboratory data). P-values less than 0.05 will be considered significant. All statistical analyses will be performed using SAS (Version 9.4; SAS Institute, Cary, NC). [name] will serve as the study statistician.

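### Safety summaries by arm would rest on 2-weekly visits in one arm and 4-weekly in the other, with no rule for time at risk or for data after cross-over

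*Combined protocol and SAP*

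**What the plan says.** Section 6.2 sets two schedules. For the combination arm, "Patients receiving study treatment will be followed every 2 weeks", with history, examination, hematology and biochemistry. For the other arm, "Patients randomized to observation will be followed every 4 weeks and the following will be done", with the same history, examination and laboratory profiles. Thyroid tests are only "for subjects receiving nivolumab". Tumor imaging is 8-weekly in both arms.

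Section 11.3 states: "All randomized subjects will consist of the safety population". It applies that population to every safety summary, laboratory data included. It does not say whether the tables will show counts, worst grades, patients ever affected, or rates.

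Section 5.1.2 says that for the observation group "cross-over at the time of disease progression will be allowed", and Section 11.1 repeats this. No section says which arm the later safety data belong to. Under Section 6.2 a patient who crosses over is receiving study treatment and so moves to 2-weekly visits.

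Section 8.3 gives both arms one reporting tail: "all adverse events will be reported until 30 days after the last dose of study treatment or last observation follow-up visit" (90 days for serious events), ending earlier if new systemic anticancer therapy starts.

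**The concern.** The proportion of patients with at least one abnormal result rises with the number of looks, and so do counts and worst grades. One arm is looked at twice as often per unit time. If the treatment works as planned, it is also looked at for longer. The observation arm is the only concurrent background rate in phase II, in patients recently off platinum chemotherapy and some recently off radiotherapy, whose laboratory changes may have causes other than study drug.

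At stake is how the safety tables can be read. Characterizing the safety of the combination is a secondary objective (Section 3.3.1), and Section 3.1 hypothesizes that it is safe and tolerable. A reader who sets the two columns side by side could not separate drug effect from visit schedule, time under observation and post-cross-over treatment.

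**Working it through.** The documents give no figure for the safety comparison, so there is none to reproduce.

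**Inputs from the documents.** Draw interval 14 days v 28 days (6.2). Scan interval 56 days in both arms (6.2). Median PFS 5 v 2 months (11.2); 2/5 = 0.4 agrees with the stated hazard ratio.

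**Assumptions.** Exponential PFS; a month of 30.4375 days; a patient stays on schedule until the scan that shows progression. The chance *p* of an abnormal result is the same at every draw in both arms, and draws are independent. The documents give no value for *p*, so a range is shown. Post-cross-over data are left out.

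**Step 1: equal 8-week follow-up.** Draws are 56/14 = 4 v 56/28 = 2. With P(ever abnormal) = 1 − (1 − p)^draws and p = 2%: 1 − 0.98⁴ = 7.8% v 1 − 0.98² = 4.0%.

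**Step 2: draws with follow-up to progression.** The number of 56-day intervals N is geometric with q = exp(−ln 2 × 56 / (median × 30.4375)) and mean 1/(1 − q).
- Median 5 months: q = 0.775, mean N = 4.44, draws 4 × 4.44 = 17.8.
- Median 2 months: q = 0.529, mean N = 2.12, draws 2 × 2.12 = 4.2.

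The ratio is 17.8/4.2 = 4.2. Frequency supplies a factor of 2.0 and time 4.44/2.12 = 2.1.

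**Step 3: patients ever abnormal.** With m draws per interval (4 v 2) and s = (1 − p)^m, P = 1 − s(1 − q)/(1 − sq). For p = 2%, s = 0.9224 v 0.9604.
- Combination, median 5: 1 − 0.9224 × 0.2251/(1 − 0.9224 × 0.7749) = 27.2%.
- Combination, median 2: 1 − 0.9224 × 0.4715/(1 − 0.9224 × 0.5285) = 15.1%.
- Observation, median 2: 1 − 0.9604 × 0.4715/(1 − 0.9604 × 0.5285) = 8.0%.

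| p per draw | 8 weeks in both arms | Median 2 months in both arms | Medians 5 v 2 months |
|---|---|---|---|
| 1% | 3.9% v 2.0% | 8.0% v 4.1% | 15.4% v 4.1% |
| 2% | 7.8% v 4.0% | 15.1% v 8.0% | 27.2% v 8.0% |
| 5% | 18.5% v 9.8% | 32.6% v 18.6% | 50.3% v 18.6% |
| 10% | 34.4% v 19.0% | 52.6% v 33.2% | 70.0% v 33.2% |

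The draw count depends on the stopping rule. If draws stop at progression itself and only completed intervals count, simulation gives 15.2 v 2.7 draws at the planned medians, and 23.3% v 5.1% ever abnormal at p = 2%.

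**Step 4: dependence on duration.** An episode of d days is caught with probability min(1, d/14) v min(1, d/28): 0.50 v 0.25 for 7 days, 1.0 v 0.5 for 14 days, 1.0 v 0.75 for 21 days, and 1.0 v 1.0 from 28 days. A rate per patient-month therefore corrects for time but not for frequency: a 14-day abnormality would still be found twice as often on the combination.

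**Step 5: common visits.** Limited to the 4-weekly visits, both arms have 2 draws in 8 weeks, and at p = 5% both show 9.8%. The proportion abnormal per draw is p in both arms in every scenario.

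**The case against.** A reader might infer that the combination must look worse by construction. The documents do not support that. Section 11.3 names no metric, and the artefact affects counts, worst grades and ever-abnormal percentages; per-draw rates are free of it under the assumptions above. Data after cross-over, if kept in the randomized arm, add treated and 2-weekly time to observation. That pushes the other way and is not in the figures above.

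A reader might also infer that observation is scheduled for a shorter time. It is not. Section 6.2 gives no stopping point for observation visits, and Section 8.3 gives both arms the same tail. The shorter time follows only from the planning medians and would vanish if PFS were equal.

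Nor do the laboratory figures carry over to adverse events. Section 8.1.1 includes patient-reported events, which can be recalled at the next visit. It counts a laboratory abnormality as an adverse event only if it has consequences or is judged to have significant clinical impact. Four-weekly adverse event assessment on observation is itself an inference from the visit schedule, because the calendar in Appendix D shows treatment cycles only.

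Finally, it does not follow that toxicity attributed to the combination is overstated. Attribution is made event by event (Section 8.1.5), not by subtracting the observation rate, and no between-arm safety test is planned.

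All of this stands, and it limits the point. Closer monitoring of treated patients is not a defect either. What remains is that Section 11.3 puts both arms into the same safety summaries without saying how unequal looking, unequal time and cross-over will be handled.

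**Conclusion.** The point holds as a cheap improvement to descriptive secondary summaries. Conventional count, worst-grade and ever-abnormal laboratory tables by arm would be unequally ascertained. With no true difference and an assumed 2% risk per independent draw, the size is about 15% v 8% from frequency alone (median 2 months in both arms) and about 27% v 8% at the planned medians. The gap depends strongly on *p* and on how long abnormalities last; frequency adds nothing for those of 28 days or more. Adverse events are less affected than laboratory values. With cross-over data unassigned, the net direction in the planned tables cannot be stated. The primary PFS comparison is untouched, since imaging is 8-weekly in both arms.

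**What to change.** Add three rules to Section 11.3.

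1. End the between-arm safety comparison at cross-over. Give adverse event incidence per patient-month at risk, with the same reporting tail in both arms. Section 8.3 already provides a common tail; the at least 100 days for nonserious events in Appendix E runs only from the last dose of study treatment and should be reconciled with it. Say whether cross-over counts as new systemic anticancer therapy under Section 8.3.
2. For laboratory data, add a between-arm table limited to the 4-weekly visits common to both arms (the day 1 and day 29 equivalents), by visit or per draw, over the whole pre-cross-over period. Limiting it to the first 8 weeks would be too narrow: Appendix D places the radioligand on day 15 of each cycle, so that window holds one administration, and the next falls on cycle 2 day 15 (56 + 15 = day 71).
3. Report all 2-weekly combination-arm data in full, and tabulate post-cross-over data separately as combination exposure.

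The cost is wording and extra tables; no new data are needed. The between-arm laboratory table omits the combination arm's day 15 and day 43 draws, which stay in the full combination tables. Later visits will also be thin on observation. If the 52 patients are split 1:1 (the ratio is not stated), about 26 × 0.529 = 14 would be progression-free at 8 weeks and 26 × 0.529² = 7 at 16 weeks, so denominators should be shown at each visit.
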